4.2. Exclusion Criteria

Subjects who meet any of the following criteria will not be allowed to participate in this study:

1. Diagnosed with WHO Group II, III, IV, V of PH.
2. Using calcium channel blockers when screening.
3. BP $> 160/100$ mmHg at Screening
4. Systolic BP < 90 mmHg at Screening
5. Pulmonary function test: FEV1 $< 60\%$ of predicted, TLC $< 60\%$ of predicted, DLCO $< 60\%$ of predicted
6. One of the following tests with confirmed pulmonary emboli and chronic thromboembolic pulmonary hypertension (CTEPH) following initial diagnosis of PAH:
 - a. Pulmonary ventilation/perfusion scan
 - b. CT pulmonary angiogram
 - c. Contrast dye pulmonary angiogram
7. History of sleep apnea
8. Limited full participation in the 6MWT due to arthritic, neuromuscular,

vascular or other diseases unrelated to PAH

9. History of acute cardiovascular and cerebrovascular events within 6 months before screening.
10. Echocardiogram (ECHO) demonstrating at least 1 of the following:
 - a. LVEF $\leq 50\%$
 - b. Mean end-diastolic left ventricular septal and posterior wall thickness of >12 mm
 - c. Left atrial (LA) area on apical 4 chamber view >20 cm 2
 - d. LA volume by biplane modified Simpsons or area-length methods >55 mL
 - e. LA volume index >29 mL/m 2
 - f. Significant valvular heart disease including moderate or severe mitral or aortic stenosis with an aortic valve area <1.0 cm 2 or mitral valve area <1.5 cm 2), greater than moderate aortic or mitral regurgitation, greater than moderate tricuspid or pulmonic stenosis
11. Restrictive, dilated or hypertrophic cardiomyopathy or constrictive pericarditis
12. Using non-oral prostacyclin when screening;
13. Laboratory parameters during screening:
 - a. Baseline aspartate aminotransferase (AST) or alanine aminotransferase (ALT) ≥ 2 times the upper limit of normal (ULN) or total bilirubin ≥ 1.5 times ULN.
 - b. Estimated glomerular filtration rate (eGFR) <60 mL/min by Cockcroft-Gault formula
 - c. Hemoglobin concentration ≤ 100 g/L at screening
14. QTc interval by Fridericia's criteria (QTcF) ≥ 500 msec at screening
15. Malignancy within 5 years before screening visit (with the exception of localized non-metastatic basal cell carcinoma of the skin, non-metastatic carcinoma of the prostate or in-situ carcinoma of the cervix excised with curative results)
16. Alcohol or drug abuse within 1 year before screening
17. A psychiatric, addictive or other disorder that compromises the ability to give informed consent for participating in this study
18. History of organ transplantation
19. Pregnant or nursing females
20. History of HIV
21. Positive hepatitis B surface antigen (HBsAg), hepatitis C antibody (HCV-Ab), or HIV antibody (HIV-ab).
22. Enrolled in another interventional study within 30 days before screening.
23. Any condition that, in the opinion of the investigator, prevents a potential subject from safely participating in the study

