10. Both male and female subjects agree to use a medically acceptable method of contraception throughout the entire study period from informed consent signing to 90 days after last dose, if the possibility of conception exists. Medically acceptable methods of contraception include oral, implantable, or injectable contraceptives (starting 2 months before dosing); diaphragm with vaginal spermicide; intrauterine device; condom and partner using vaginal spermicide; and surgical sterilization (6 months after surgery). Women who are surgically sterile or those who are postmenopausal for at least 2 years are not considered to be of childbearing potential. Eligible male and female subjects must agree not to participate in a

conception process (i.e. active attempt to become pregnant or to impregnate, sperm donation, in vitro fertilization) during the study and for 90 days after the last dose of study drug.

11. Body weight no less than 40 kg at Screening.
12. Able to understand and willing to sign the Informed Consent Form (ICF) and comply with the study procedures.

Exclusion Criteria

Subjects who meet any of the following criteria will not be allowed to participate in this study:

1. Diagnosed with WHO Group II, III, IV, V of PH;
2. Using calcium channel blockers when Screening;
3. BP>160/100mmHg at Screening;
4. Systolic BP <90 mmHg at Screening;
5. Pulmonary function test: FEV1<60% of predicted, TLC<60% of predicted, DLCO<60% of predicted;
6. One of the following tests with confirmed pulmonary embolism and/or chronic thrombo-embolic pulmonary hypertension (CTEPH) following initial diagnosis of PAH:
 - a. Pulmonary ventilation/perfusion scan
 - b. CT pulmonary angiogram
 - c. Contrast dye pulmonary angiogram
7. History of sleep apnea.
8. Limited full participation in the 6MWT due to arthritic, neuromuscular, vascular or other diseases unrelated to PAH.
9. History of acute cardiovascular and/or cerebrovascular events within 6 months before screening.
10. Echocardiogram (ECHO) demonstrating at least one of the following:
 - a. LVEF $\leq 50\%$
 - b. Mean end-diastolic left ventricular septal and posterior wall thickness of >12 mm
 - c. Left atrial (LA) area on apical 4 chamber view >20 cm^2
 - d. LA volume by biplane modified Simpsons or area-length methods >55 mL
 - e. LA volume index >29 mL/m 2

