8.2. Determination of Sample Size

No formal statistical assessment, in terms of sample size, has been conducted. Approximately 36 subjects will be randomized into 3 treatment cohorts with GMA301-assigned subjects receiving either 300, 600, or 1000 mg injections of the study drug depending on their assigned cohort. Each cohort will include 12 subjects, 9 of whom will be administered active GMA301 and 3 of whom will receive placebo.

The number of subjects in each cohort of the present study is common in early clinical pharmacology studies and is considered sufficient to achieve the objectives of the study.

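### Exclusions 6 and 9 read *and/or* in the Synopsis but *and* in Section 4.2, so the protocol carries two eligibility rules that can give different answers for the same subject

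*Combined protocol and SAP*

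**What the plan says.** Section 4.2 opens its list with "Subjects who meet any of the following criteria will not be allowed to participate in this study", so a single criterion is enough to bar a subject. The Synopsis list works the same way.

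**Criterion 6** (ventilation/perfusion scan, CT angiogram or contrast angiogram):
- Section 4.2: "confirmed pulmonary emboli and chronic thromboembolic pulmonary hypertension (CTEPH) following initial diagnosis of PAH"
- Synopsis: "confirmed pulmonary embolism and/or chronic thrombo-embolic pulmonary hypertension (CTEPH) following initial diagnosis of PAH"

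**Criterion 9** (recent events):
- Section 4.2: "History of acute cardiovascular and cerebrovascular events within 6 months before screening"
- Synopsis: "History of acute cardiovascular and/or cerebrovascular events within 6 months before screening"

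Two other Section 4.2 exclusions bear on the same patients. Exclusion 1 is "Diagnosed with WHO Group II, III, IV, V of PH". Exclusion 23 is "Any condition that, in the opinion of the investigator, prevents a potential subject from safely participating in the study".

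On scale, Section 8.2 says: "Each cohort will include 12 subjects, 9 of whom will be administered active GMA301 and 3 of whom will receive placebo".

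**The concern.** Eligibility text decides who is dosed. A site working from the Synopsis and a site working from Section 4.2 could reach opposite decisions on the same patient and both be following the protocol. The patients in question have confirmed pulmonary emboli without CTEPH or, on one reading, an acute cardiovascular or cerebrovascular event of only one kind in the six months before screening.

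This matters because safety in Group 1 PAH is the primary objective and Week 12 right-heart-catheter measurements are secondary endpoints. Admitting such patients at some sites and not at others would make the population uneven. It could also expose patients whom one version of the protocol sets out to keep off study drug.

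**Working it through.** The plan has no figure to reproduce on this point, so the check is a comparison of texts followed by simple arithmetic for scale.

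**Step 1: are both texts current?** The Summary of Amended Protocol Changes lists Section 4.2 edits to criteria 5 and 10 only. It also says that the Synopsis was brought into line with the body where applicable. Nothing marks either version of criteria 6 or 9 as superseded.

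**Step 2: criterion 6, case by case, with *and* taken literally.**

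| Imaging finding | Synopsis 6 | Section 4.2(6) | Exclusion 1 |
|---|---|---|---|
| Emboli and CTEPH | excluded | excluded | excluded (WHO Group IV) |
| CTEPH only | excluded | not excluded | excluded (WHO Group IV) |
| Emboli only | excluded | **not excluded** | not clearly covered |

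The first two rows are settled by exclusion 1. Inclusion 2 supports this by requiring Group 1 PAH, and the Introduction separates Group 1 from chronic thromboembolic disease. On the literal reading, then, Section 4.2(6) adds little to exclusion 1, and the third row is a direct conflict with the Synopsis.

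**Step 3: criterion 9, under both readings of Section 4.2.**

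| Events in the 6 months before screening | Synopsis 9 | Section 4.2(9), both required | Section 4.2(9), list of two event types |
|---|---|---|---|
| Both kinds | excluded | excluded | excluded |
| Cardiovascular only | excluded | not excluded | excluded |
| Cerebrovascular only | excluded | not excluded | excluded |

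Section 4.2 supports either reading; the Synopsis supports only one. Elsewhere in Section 4.2 the authors are explicit when one item suffices: criterion 10 says so in its lead-in and criterion 13a uses *or*. A strict reader could therefore take *and* in criterion 9 to mean both.

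**Step 4: what else would catch these patients?**
- Inclusion 5 requires no disease worsening over at least 3 months before screening. Criterion 9 looks back 6 months, so at least 6 − 3 = 3 months may lie outside that window, and an event need not count as worsening of PAH.
- Inclusion 9 concerns new IV diuretic, cardiotonic or vasoactive drugs in the previous 30 days only.
- Exclusion 10 catches those whose echocardiogram meets one of its listed findings.
- Exclusion 23 could catch any of them, but it rests on the investigator's opinion and on safe participation, not on whether the hemodynamic data can be interpreted.

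Coverage is partial and, for exclusion 23, discretionary. The Synopsis plans about 7 + 3 = 10 sites in China and the United States.

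**Step 5: scale.** Total: 3 × (9 + 3) = 36, as stated. One affected subject is:
- 1/9 = 11.1% of a dose group;
- 1/3 = 33.3% of the placebo subjects in one cohort;
- 1/(3 × 3) = 11.1% of placebo if pooled across cohorts (the protocol does not say whether it will be).

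A single such subject is allocated to active drug with probability 9/12 = 0.75. The documents give neither the frequency of such patients nor the size of any change they would show, so the calculation stops here.

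**The case against.** The strongest reply is that this is a wording slip with little practical effect. Criterion 9 in Section 4.2 reads naturally as a list of two event types. The other criteria remove some of the patients concerned, and few investigators would enrol the rest. The English text follows a Chinese protocol that is not available here, and about 7 of the 10 sites are in China, so what most sites actually apply is unknown. The Schedule of Assessments lists no ventilation/perfusion scan or pulmonary angiogram, so wording alone does not guarantee that criterion 6 is checked.

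Much of that stands. Criterion 9 is ambiguous, the overlap with other criteria is real, and the effect on enrolment cannot be established. It does not remove the conflict over criterion 6, where the literal difference is plain, and the Synopsis version of criterion 9 leaves no matching ambiguity.

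A reader might also infer three stronger things that the documents do not support:
- *That Section 4.2 admits these patients outright.* It fails to bar them only through criterion 6 read literally, or criterion 9 on one of its two readings. Other criteria may still apply.
- *That the Week 12 hemodynamic or safety results would be confounded.* Allocation is randomized within cohort, hemodynamics are compared with baseline, and Section 8.1 plans description without testing. The realistic effect is noise and chance imbalance in small groups. Any figure for a shift in mean PVR would rest on an invented individual change.
- *That one such patient moves a cohort towards discontinuation under Section 3.6.* That rule counts discontinuations for events that investigators judge drug-related, and Appendix 1 provides a category for events caused by the subject's clinical state. The inference assumes misattribution.

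**Conclusion.** The point holds as an internal contradiction in operative eligibility text. It is clear for criterion 6: a subject with confirmed emboli and no CTEPH is excluded by the Synopsis and not by Section 4.2(6) as literally worded. For criterion 9 it is a conflict between an unambiguous text and an ambiguous one. The consequences are possible inconsistent enrolment between sites, a possible patient-safety gap, and added noise in groups of 9 active and 3 placebo per cohort. The 11.1% and 33.3% shares show how much weight one subject carries; they do not estimate bias. The conclusion assumes that sites may rely on either part of the English protocol and that the Chinese version, not seen here, does not already settle the matter. The documents do not show which wording was intended, and this review takes no position on it.

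**What to change.** Reconcile the Synopsis and Section 4.2 so that exclusions 6 and 9 are identical in both. Each should state explicitly whether either condition alone excludes a subject or whether both must be present. Before editing, the sponsor should confirm the intended rule and check the corresponding criteria in the Chinese protocol, so that all sites work to one text.

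The cost is a few words in an amendment plus a note to sites. Sample size, endpoints and analyses need no change. Depending on the rule confirmed, a few patients whom one version would have admitted may become ineligible, or the reverse. If anyone has already been screened, the sponsor should check whether the two wordings gave different answers for them.

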4.3. Subject Number and Identification

Subjects will have unique identification numbers used at Screening and randomization. Assignment of subject numbers will be in ascending order and no numbers will be omitted.

All study documentation will be identified by Screening number only. A list identifying the subjects by subject number will be kept in the Site Master File.

5. STUDY DRUGS

5.1. Description, Storage, Packaging, and Labeling

The IMPs (300, 600, and 1000 mg GMA301 Injection) and their matching placebos will be supplied by the Sponsor, along with the batch/lot numbers and Certificate of Analysis. The IMP will be provided in glass vial and stored according to the instructions on the label.

The placebo treatment will be composed of the same ingredients as the GMA301. The appearance of the placebos should be identical to either GMA301, to ensure the study is blinded.

All IMPs will be stored at the study site in a location that is locked with restricted access.

The bulk drug container and unit dose containers will be labeled in accordance with national laws and regulations. The IMPs will be transferred from bulk supplies into the subject's dose container by qualified clinical staff.

GMA301 and placebo injections should be stored at 2~8°C and protected from direct sunlight. Protection from light is not required during preparation and injection.

5.2. Study drug Administration

The 300, 600, and 1000 mg doses of GMA301 and matching placebo will be administered Q4W via IV injection by slow push for 12 weeks.

The study drug will be injected at an approximate rate of no more than 4 mL/min. The syringes should be connected to the previously inserted cannula for administration.

5.3. Randomization

An IWRS will be used to randomly assign subjects to treatments. Nine subjects per cohort will be randomly assigned to active GMA301 and three subjects per cohort will be randomly assigned to receive placebo.

5.4. Blinding

The following controls will be employed to maintain the double-blind status of the study:

The placebo will be identical in appearance to the GMA301.

The Investigator and other members of staff involved with the study will remain blinded to the treatment randomization code during the assembly procedure.

5.5. Treatment Compliance

The following measures will be employed to ensure treatment compliance:

All doses will be administered by suitably qualified study site staff.

At each dosing occasion, a pre-dose and post-dose inventory of IMP will be performed.

5.6. Drug Accountability

The Investigator (or designee) will maintain an accurate record of the receipt of the study supplies received. In addition, an accurate drug dispensation record will be kept, specifying the amount dispensed to each subject and the date of dispensing. This drug accountability record will be available for inspection at any time. At the completion of the study, the original drug accountability record will be available for review by the Sponsor upon request.

For each batch of unit doses, the empty used unit dose containers will be discarded upon satisfactory completion of the compliance and accountability procedures. Any unused assembled unit doses will be retained until completion of the study.

At the completion of the study, all unused supplies will be returned to the Sponsor or disposed of by the study site, per the Sponsor's written instructions.

6. CONCOMITANT THERAPIES AND OTHER RESTRICTIONS

6.1. Concomitant Therapies

Subjects will refrain from use of any prescription or nonprescription medications/products during the study until the Follow-up visit, unless the Investigator (or designee) and/or Sponsor have given their prior consent.

The administration of any concomitant medications during the study is prohibited without prior approval of the investigator. Any medication taken by a subject during the study and the reason for its use will be documented in the source data.

6.2. Diet

Subjects will be fasted at least 8 hours and cannot drink water for 2 hours before any blood sample collections for safety examination purpose.

Consumption of alcohol will not be permitted from 48 hours prior to Screening to the last follow-up visit.

6.3. Smoking

Subjects will not be permitted to use tobacco- or nicotine-containing products within 3 months prior to Screening until the last follow-up visit.

6.4. Exercise

Subjects are required to refrain from intensifying strenuous exercise from 7 days before screening until the Follow-up visit, but will otherwise maintain their normal level of physical activity during this time (ie, will not begin a new exercise program nor participate in any unusually strenuous physical exertion).

7. STUDY ASSESSMENTS AND PROCEDURES

Where activities at a given timepoint coincide, consideration must be given to ensure that the following order of activities is maintained: ECGs, vital signs, and blood drawings.

7.1. Pharmacokinetic Assessments

7.1.1. Sample Collection and Processing

Blood samples will be collected by venipuncture or cannulation at the times indicated in the Schedule of Assessments in [Appendix 6](#).

Up to 3 additional blood samples may be taken from each subject per treatment period, with the maximum volume of blood withdrawn per subject not exceeding the limit detailed in [Appendix 3](#). Any changes to the scheduled times of PK assessments will be agreed with the Sponsor and documented in the TMF.

7.1.2. Analytical Methodology

Serum concentrations of GMA301 will be determined using validated analytical procedures. Specifics of the analytical methods will be provided in separate documents.

7.2. Safety and Tolerability Assessments

7.2.1. Adverse Events

AE definitions, assignment of severity and causality, and procedures for reporting SAEs are detailed in [Appendix 1](#).

The condition of each subject will be monitored from the time of signing the ICF to final discharge from the study. Subjects will be observed for any signs or symptoms and asked about their condition by open questioning, such as “How have you been feeling since you were last asked?”, at least once each day while resident at the study site and at each study visit. Subjects will also be encouraged to spontaneously report AEs occurring at any other time during the study.

All non-serious AEs, whether reported by the subject voluntarily or upon questioning, or noted on physical examination, will be recorded from initiation of study drug until study completion. Serious AEs will be recorded from the time the subject signs the ICF until study completion. The nature, time of onset, duration, and severity will be documented, together with an Investigator’s (or designee’s) opinion of the relationship to study drug.

AEs recorded during the course of the study will be followed up, where possible, until resolution or until the unresolved AEs are judged by the Investigator (or designee) to have stabilized. This will be completed at the Investigator’s (or designee’s) discretion.

The Adverse Event(s) related to RHC is listed in the separated document.

7.2.2. Clinical Laboratory Evaluations

Blood and urine samples will be collected for clinical laboratory evaluations (including clinical chemistry, hematology, urinalysis, and serology) at the times indicated in the Schedule of Assessments in [Appendix 6](#).

Clinical laboratory evaluations are listed in [Appendix 2](#). Additional clinical laboratory evaluations will be performed at other times if judged to be clinically appropriate or if the ongoing review of the data suggests a more detailed assessment of clinical laboratory safety evaluations is required.

For females of reproductive potential, a pregnancy test will be performed at the times indicated in the Schedule of Assessments in [Appendix 6](#).

An Investigator (or designee) will perform a clinical assessment of all clinical laboratory data.

7.2.3. Vital Signs

Seated blood pressure, seated pulse rate, respiratory rate, and body temperature will be assessed at the times indicated in the Schedule of Assessments in [Appendix 6](#).

Vital signs may also be performed at other times if judged to be clinically appropriate or if the ongoing review of the data suggests a more detailed assessment of vital signs is required.

Day 1 pre-dose blood pressure, pulse rate, and respiratory rate will be measured in triplicate at approximately 2-minute intervals. The mean value will be used as the baseline value in the data analysis. All subsequent measurements will be performed singly and repeated once if outside the relevant clinical reference ranges. Body temperature will be measured singly.

Subjects must be seated or lie for at least 5 minutes before blood pressure and pulse rate measurements.

7.2.4. Electrocardiogram

7.2.4.1. 12-Lead Electrocardiogram

A resting 12-lead ECG will be recorded after the subject has been supine and be seated or lie for at least 5 minutes at the times indicated in the Schedule of Assessments in [Appendix 6](#).

ECGs will be recorded at screening, Week 4, Week 8, and Week 12.

The 12-lead ECGs will be repeated 3 times, and an average taken of the 3 readings. The QTcF will be averaged and any subject meeting the following criteria will have study medication held and will be followed up:

- QTcF value >500 msec
- QTcF change from the baseline (predose) >60 msec.
- Second- or third-degree heart block or bundle branch block

Additional 12-lead ECGs may be performed at other times if judged to be clinically appropriate or if the data suggests a more detailed assessment of ECGs is required. The investigator (or designee) will perform a clinical assessment of each 12-lead ECG.

Day 1 pre-dose 12-lead ECGs will serve as the baseline assessment. The mean values of PR, QRS, and QTcF will be entered into the eCRF. Averaged values for subsequent ECG intervals should also be entered into the eCRF.

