3.6. Stopping and Subjects withdraw Criteria

The following criteria will result in immediate discontinuation of the subject dosing:

- An SAE that is related to GMA301;
- QTcF >500 msec or extension 60 msec against baseline.
- Liver function test abnormalities for severe liver injury (based upon US FDA “Guidance for Industry, Drug-Induced Liver Injury: Premarketing Clinical Evaluation”, July 2009):
 - Alanine aminotransferase (ALT) or aspartate aminotransferase (AST)>3x upper limits of normal (ULN) with total bilirubin > 2X ULN (Hy’s Law)
 - ALT or AST >3x ULN with international normalized ratio (INR)>1.5
 - ALT or AST >8X ULN
 - ALT or AST >5X ULN persisting for more than 2 weeks
 - ALT or AST >3x ULN or 3 times baseline value with the appearance of fatigue, nausea, vomiting, right upper quadrant pain or tenderness, fever, rash and/or eosinophilia (>5%)

Close follow-up of subjects must be organized in any of the above cases including:

- Repeating liver enzyme and serum bilirubin tests 2 or 3 times weekly. Frequency of retesting can decrease to once a week or less if abnormalities stabilize or the trial drug has been discontinued and the subject is asymptomatic.
- Obtaining a more detailed history of symptoms and prior or concurrent diseases
- Obtaining a history of concomitant drug use (including non-prescription medications and herbal and dietary supplement preparations), alcohol use, recreational drug use, and special diets.
- Ruling out acute viral hepatitis types A, B, C, D, and E; autoimmune or alcoholic hepatitis; non-alcoholic steatohepatitis; hypoxic/ischemic hepatopathy; and biliary tract disease.
- Obtaining a history of exposure to environmental chemical agents.
- Obtaining additional tests to evaluate liver function, as appropriate (e.g., INR, direct bilirubin)
- Obtaining gastroenterology or hepatology consultations

If a treatment-related SAE is suspected by investigators, immediate discontinuation of study drug must occur and medical care must be applied and the case immediately reported to the SRC. An ad hoc SRC meeting will be organized to make decisions for the study accordingly.

A subject is free to withdraw from the study at any time. A subject is requested to withdraw by the investigators if any of the following criteria are met:

- Subjects' non-compliance with the study procedure that might affect subject safety or study assessments/objectives, by the investigators

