- Any clinically relevant sign or symptom (eg, Class IV heart failure) that, in the opinion of the Investigator (or designee), warrants subject withdrawal.

Subject who didn't get IMP treatment within protocol defined timeline with any reason can get back to the IMP treatment with investigator or SRC's evaluation and agreement.

All the discontinuation must be documented accordingly. If a subject is withdrawn, the Sponsor will be notified in 24 hours and the date and reason(s) for the withdrawal will be documented in electronic Case Report Form (eCRF). In this case, efforts in any ways must be made to complete the follow up assessments. ([Appendix 6](#)). Other medical procedures may be performed at the Investigator's discretion. The Investigator may also request subjects to return for additional Follow-up visits. All AEs will be followed until recovery or stabilization.

Cohort discontinuation and study termination

The SRC will discontinue or stop the cohort or even the study in case of :

- Two cases discontinuations in a cohort due to events related to the study drug under the diagnosis of the investigators;
- Single case with severe allergic event related to study drug;
- Known and expected AEs are with increased frequency, severity and or long lasting.

The sponsor can terminate the study with notification to the investigators.

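### Section 7.2.4.1 only holds study drug for a QTcF event that Section 3.6 says stops dosing, and the return-to-treatment sentence leaves a way to re-dose the subject

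*Combined protocol and SAP*

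**What the plan says.** Section 3.6 opens its list of individual stopping criteria with "The following criteria will result in immediate discontinuation of the subject dosing" and includes in that list "QTcF >500 msec or extension 60 msec against baseline".

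Section 7.2.4.1 has three ECG recordings averaged and then says that "any subject meeting the following criteria will have study medication held and will be followed up". Its criteria are QTcF above 500 msec, "QTcF change from the baseline (predose) >60 msec", and heart block of second or third degree or bundle branch block. It also provides that "Additional 12-lead ECGs may be performed at other times if judged to be clinically appropriate", so a case can come to light between scheduled visits.

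Later in Section 3.6, a subject who was not treated "within protocol defined timeline with any reason can get back to the IMP treatment with investigator" or, alternatively, SRC (Safety Review Committee) evaluation and agreement.

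Under its cohort and study termination heading, Section 3.6 has the SRC act on "Two cases discontinuations in a cohort due to events related to the study drug under the diagnosis of the investigators". Another listed trigger is "Known and expected AEs are with increased frequency, severity and or long lasting".

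**The concern.** Stopping and holding are different instructions. A stop ends the subject's exposure. A hold suggests that dosing may resume, and one with no release rule leaves the site to decide when. Two sites with the same averaged QTcF could act differently, depending on which section they work from. The investigator reading an ECG is most likely to have the ECG section open, and that section carries the weaker instruction.

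Two things are at stake. The first is the subject: a further dose could be given after a QTcF finding that the protocol elsewhere treats as a reason to stop. The second is the cohort rule, which counts discontinuations. A case entered as a hold may not be recorded as one. Safety is the primary objective, and the earlier human study described in Section 1.5.1 gave single doses to healthy subjects, so the individual and cohort stopping rules should be free of contradiction.

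**Working it through.** The protocol gives no figure on this point to reproduce. The check is a comparison of the texts, followed by three short calculations.

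**Step 1. The two rules side by side.**

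| Element | Section 3.6 | Section 7.2.4.1 |
|---|---|---|
| Absolute limit | QTcF above 500 msec | QTcF above 500 msec |
| Change limit | 60 msec, no inequality sign | more than 60 msec |
| Reference value | baseline | Day 1 predose |
| Reading used | not stated | mean of three |
| Action | dosing discontinued at once | medication held, subject followed up |
| Release rule | none specific to QTcF | none |
| Heart block, bundle branch block | not listed | held |

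**Step 2. Is it the same event?** Every QTcF case under 7.2.4.1 also meets 3.6: an averaged value above 500 msec is above 500 msec, and an averaged rise of more than 60 msec has reached 60 msec. The reverse can fail only at the edges, namely a rise of exactly 60 msec, or a single reading over the limit when the average is not. So for every QTcF case that 7.2.4.1 holds, 3.6 requires a stop.

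**Step 3. Is there a way back to dosing?** Section 7.2.4.1 states none. The return sentence in 3.6 is the only one. It applies whatever the reason for the missed treatment, does not except the QTcF criterion, sets no recovery value, and accepts the investigator's agreement as an alternative to the SRC's. The scheduled SRC review in Section 3.5 takes place after eight subjects have had three doses and 28 days of follow-up, so it is not timed to settle a re-dosing question at Week 4 or Week 8.

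**Step 4. Doses affected.** Doses are given at Weeks 0, 4 and 8 (Section 3.1).
- Case found before the Week 4 dose: 3 − 1 = 2 of 3 doses in question.
- Case found after the Week 4 dose and before the Week 8 dose: 3 − 2 = 1 of 3.
- Case found at the Week 12 ECG: 3 − 3 = 0, so the conflict has no dosing consequence.

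**Step 5. How long a further dose lasts.** Section 1.5.2 reports mean terminal half-lives of 503.75 to 565.63 hours and mostly mono-exponential decline. The fraction left after one 28-day interval (672 hours) is 0.5^(672/half-life):
- 0.5^(672/503.75) = 0.5^1.334 = 0.40
- 0.5^(672/565.63) = 0.5^1.188 = 0.44

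If the healthy-subject half-life carries over to patients, about 40% to 44% of a mistaken dose remains four weeks later.

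**Step 6. Cohort rule.** The threshold is two drug-related discontinuations in a cohort. One case not recorded as a discontinuation is 1/2 of it.

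**The case against.** The best defence is that the sections can be read together. Under both, the next dose is withheld. Section 3.6 is the mandatory stopping section, so a site following the whole protocol would hold at the ECG and then discontinue. That reading is possible, but nothing in the text says it: 3.6 requires immediate action, and 7.2.4.1 neither points to 3.6 nor describes the hold as a first step.

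The return sentence may also have been meant for late or missed visits. That is plausible, but its wording is not so limited. This part of the objection does show that changing the verb in 7.2.4.1 is not enough by itself, because the return sentence sits in 3.6 and must be dealt with there.

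Three stronger readings are tempting, and the documents do not support them.
- **That 7.2.4.1 authorises re-dosing.** It does not. It is silent on resumption, and the only route is the general sentence in 3.6.
- **That QTcF cases fall outside the two-case rule.** Section 3.6 already classes the event as a discontinuation. A case is missed only if a site follows 7.2.4.1 instead, and it counts only if the investigators judge it drug-related. The SRC also reviews ECG data and can act on worsening adverse events, and its charter, which is not in these documents, may settle the counting.
- **That the chance of the cohort rule failing can be calculated.** It depends on an assumed event rate. With 9 active subjects, other drug-related discontinuations at 2% and QTcF cases at rate e, all assumed and independent, p = 1 − 0.98(1 − e) and P(at least two) = 1 − (1 − p)^9 − 9p(1 − p)^8. This is 1.3% with QTcF cases uncounted. With them counted it is 1.4% at e = 0.1% and 28.8% at e = 10%. The answer simply reflects the chosen rate. Section 1.5.1 names headache, nausea and pharyngitis as the most frequent events and offers no basis for choosing one.

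**Conclusion.** The contradiction is real and lies in the current text of both sections. For essentially the same QTcF event one section stops dosing and the other holds it without a release rule, while the return sentence leaves a route by which a subject whom 3.6 stops could be dosed again.

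Confidence is high on the textual conflict. The consequences are conditional: they require a site to act on 7.2.4.1 rather than 3.6, and the effect on the cohort rule also requires a drug-related judgement. The size is bounded by the dose counts in Steps 4 and 6; frequency is unknown. The point should be fixed. It does not imply that a QT signal exists or that the cohort rule is inoperative. Nor is stop or hold an open choice to be weighed afresh, since 3.6 already states the stricter rule.

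**What to change.** 1. In 7.2.4.1, state that averaged triplicate QTcF above 500 msec, or more than 60 msec above Day 1 predose, means that dosing is discontinued under 3.6.
2. Put the same thresholds, reference value and averaging rule in 3.6. This settles the difference between 60 and more than 60 msec; a rise of exactly 60 msec would then not be a trigger in either section.
3. Exclude subjects stopped on the QTcF criterion from the return-to-treatment sentence.
4. Confirm in the cohort rule that such a case counts if judged drug-related.
5. State in 3.6 the action for heart block or bundle branch block. At present these appear only in 7.2.4.1, as a hold with no release rule. If a hold is intended, say who may release it and on what finding.

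The cost is amendment wording in two sections, with no new visits, subjects or data. A cohort pause becomes slightly more likely. Exclusion 14 bars only a screening QTcF of 500 msec or more, so a subject who entered just under the limit may stop after a small rise: for example, 495 + 6 = 501 msec. That follows from the existing 3.6 rule, but consistent application will make it more visible.
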